#### **8.7.1.2 Anti hGH antibodies**

Anti-hGH antibodies in subjects randomised to Norditropin® will be analysed by a special laboratory using a validated binding antibody assay.

### **8.8 Patient reported Outcomes**

The following Patient reported outcome questionnaires would be collected in the trial:

- GHD-CIM (Growth Hormone Deficiency – Child Impact Measure)
- GHD-CTB (Growth Hormone Deficiency – Child Treatment Burden)
- GHD-PTB (Growth Hormone Deficiency – Parent Treatment Burden)

Title	Time frame	Unit
Change in GHD-CIM (domain and total scores)	From Baseline (Week 0) to visit 5 (Week 26), Baseline (Week 0) to Week 52	-100 to 100
GHD – CTB (domain and total scores)	At visit 5 (Week 26) At visit 7(Week 52)	0 to 100
GHD – PTB (domain and total scores)	At visit 5 (Week 26) At visit 7(Week 52)	0 to 100

Data from paper PRO's should be transcribed into eCRF. Please refer to protocol flow chart [1.2](#) for frequency of the assessments. Investigator must review the PRO's and discuss with the subject if there are any discrepancies observed and must document the discussion in the subject medical records.

## **8.9      Diary**

Paper diaries will be used in the trial and diary will be dispensed for the first time at randomisation, Investigator / delegated site staff must train the subject/LAR on diary completion and should instruct the subject to return the diary at the next site visit. Last diary will be dispensed at visit 6 and must be collected at visit 7.

Entries in the diaries are only to be made by the subject/LAR/Parent, unless otherwise specified. Any discrepancy must be discussed with the subject and documented in the subject medical records.

## 9 Statistical considerations

### 9.1 Statistical hypotheses

Hypothesis testing for the primary endpoint will be done by testing  $H_0: D \leq -2 \text{ cm/year}$  vs  $H_A: D > -2 \text{ cm/year}$ , where  $D$  is the mean treatment difference (smapacitan – Norditropin®). Non-inferiority of somapacitan will be considered confirmed if the lower boundary of the two-sided 95% confidence interval is above -2 cm/year. As only one confirmatory hypothesis is to be tested, no further control for multiplicity is needed.

### 9.2 Sample size determination

Approximately 108 subjects will be randomly assigned to trial product.

The sample size calculation is based on the primary estimand. It is expected based on phase 2 trial data (NN8640-4172) that the proportion of subjects with no landmark visit data or who discontinued randomised treatment before landmark visit is 10% with similar withdrawal reasons in the two treatment arms. NN8640-4172 is a global trial, including Japanese subjects, and therefore trial information from 4172 is expected to also be of use when planning for a somapacitan phase 3 trial in China. It is expected that subjects discontinuing their randomised treatment will start on ancillary treatment, if no medical reasons prohibit this. Thus, data assessed after discontinuation of the randomised treatment will not be used for the primary analysis of the primary endpoint based on the primary estimand. Assuming the same proportions of subjects with no landmark visit and subjects discontinuing randomised treatment but have landmark visit data in the two arms leads to the following sample size calculation.

The sample size is determined using a non-inferiority margin of -2.0 cm/year and a one sided two-group t-test with a significance level of 2.5% for a 2:1 randomisation ratio between somapacitan and Norditropin®.

Based on data from NN8640-4172, a standard deviation for HV at week 52 was chosen ( $SD=2.6 \text{ cm/year}$ ) for the sample size calculation giving a sample size of 108 subjects. Different SD scenarios with power calculation for the primary analysis are presented in the table below under the assumption of a true difference in annualized HV of 0 cm/year between the two treatment arms.

**Table 9      Calculated power with 108 subjects randomised 2:1**

SD	2.5 cm/year	2.6 cm/year	2.7 cm/year	2.8 cm/year
	95%	94%	92%	90%

The SD candidates are based on reported SD values from clinical trials: Valtropin phase 3 trial, 52 weeks (SD=2.8, 3.0), OPKO phase 2 trial, 52 weeks (SD=2.1, 2.3, 2.6, 3.5), and NN8640-4172, phase 2 trial, 52 weeks (SD=2.3, 2.6).

For sensitivity analysis, a one-way tipping point analysis is planned. Based on a penalty of 2 cm/year for subjects in the somapacitan arm who have missing landmark visit data or discontinue randomised treatment before landmark visit, this gives a power of ~92% (adjusted treatment effect  $0.9*0 - 0.1*2 = -0.2$ ).

If the per protocol analysis set (PP) is assumed to consist of ~85% of the trial subjects (same proportion across treatment groups), giving 60 subjects in the somapacitan arm and 30 subjects in the Norditropin® arm, then repeating the primary analysis based on the primary estimand on the PP should result in a power of 92% for confirming non-inferiority of somapacitan compared to Norditropin®, under the assumption of no true treatment difference between the two treatments.

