Let  $\delta$  be defined as the difference between the mean of the observed data and the mean of the unobserved data  $\mu_{\text{obs}} - \mu_{\text{unobs}}$ , adjusted for other observed data. Under an MAR analysis,  $\delta$  is assumed to be 0. Positive values of  $\delta$  indicate that subjects with missing endpoint values have smaller HV than subjects with observed endpoint values. If subjects primarily withdraw or discontinue randomised treatment/start ancillary therapy due to a perceived lack of efficacy, then this could be the most likely direction of departure from MAR. Let  $f_1$  and  $f_0$  be the fractions of subjects with unobserved endpoint data in the somapacitan and Norditropin® arms, respectively. The sensitivity analysis is done by subtracting a quantity  $\Delta$  from the treatment effect estimate under the MAR assumption, where  $\Delta = f_1\delta$  if data depart from MAR in the somapacitan arm only,  $\Delta = -f_0\delta$  if data depart from MAR in the Norditropin® arm only, and  $\Delta = (f_1 - f_0)\delta$  if data depart from MAR in the same way in both arms. The calculations for the 3 scenarios will use a range of  $\delta$  values increasing from 0 until the resulting 95% CI no longer is completely above -2cm/year for the most conservative evaluation (data depart from MAR in the somapacitan arm only) and the approximation that the standard error of the treatment difference is unaffected by the sensitivity analysis. All subjects from the FAS can be viewed as included in this analysis as subjects with missing endpoint data will be contributing to one of the fraction values  $f_1$  and  $f_0$ .

An analysis of the primary endpoint using the same analysis model as was used for the primary analysis under the primary estimand but based on PP instead of FAS will be conducted as a supplementary analysis.

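### The ~92% power given for the tipping-point analysis does not fit Table 9; on Table 9's basis it is about 89%

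*Protocol*

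**What the plan says.** Protocol 9.2, repeated in SAP 5, sets out the power calculation as follows.

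- **Size:** "Approximately 108 subjects will be randomly assigned to trial product", which at 2:1 is 72 somapacitan and 36 Norditropin.
- **Test:** a "one sided two-group t-test with a significance level of 2.5% for a 2:1 randomisation ratio", margin -2.0 cm/year, SD 2.6 cm/year, true difference 0.
- **Loss:** it expects that "the proportion of subjects with no landmark visit data or who discontinued randomised treatment before landmark visit is 10" per cent. Data collected after stopping randomised treatment are not used in the primary analysis. The loss is taken as equal across arms: "Assuming the same proportions of subjects with no landmark visit and subjects discontinuing randomised treatment but have landmark visit data in the two arms".
- **Primary power (Table 9):** 95%, 94%, 92% and 90% at SD 2.5, 2.6, 2.7 and 2.8.
- **Tipping-point power:** a 2 cm/year penalty in the somapacitan arm moves the effect to 0.9 × 0 - 0.1 × 2 = -0.2. For children "who have missing landmark visit data or discontinue randomised treatment before landmark visit, this gives a power of ~92" per cent.
- **Per-protocol power:** 92%, with the reduced set "giving 60 subjects in the somapacitan arm and 30 subjects" in the Norditropin arm.

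Protocol 9.4.2 and SAP 4.2.3.1 define the tipping-point analysis as a shift of the missing-at-random estimate, using "the approximation that the standard error of the treatment difference is unaffected by the sensitivity analysis".

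Neither document states the number per arm behind Table 9 or behind the ~92%.

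**The concern.** The tipping-point analysis moves the point estimate and leaves the standard error alone. Its power should therefore follow from Table 9 by one change only: the distance from the assumed effect to the margin falls from 2.0 to 1.8 cm/year. A fall from 94% to only ~92% looks too small for that change.

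The likely explanation is that the 10% loss was used to shift the effect but not to reduce the precision. If so, the section reports three powers side by side on two different bases. A reader would then think the planned trial is more robust to departures from missing at random than its own assumptions imply.

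**Working it through.** **Inputs (Protocol 9.2, SAP 5).** Margin -2.0; one-sided alpha 2.5%; SD 2.6 unless stated; 72/36 randomised; 10% loss per arm, which gives 64.8/32.4 (64/32, 65/32 or 65/33 in whole children); effect 0 for the primary analysis and -0.2 for the tipping point.

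**Formula.** SE = SD × √(1/n1 + 1/n0); noncentrality = (2 + effect)/SE; power from the noncentral t with n1 + n0 - 2 degrees of freedom.

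**Step 1: which sample size lies behind Table 9 (effect 0)?**

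| n per arm | SD 2.5 | SD 2.6 | SD 2.7 | SD 2.8 |
|---|---|---|---|---|
| Table 9 as stated | 95% | 94% | 92% | 90% |
| 72/36 (no loss) | 97.3% | 96.2% | 94.9% | 93.4% |
| 64/32 (10% loss) | 95.5% | 94.0% | 92.3% | 90.4% |
| 65/32 (10% loss) | 95.6% | 94.1% | 92.4% | 90.6% |
| 65/33 (10% loss) | 96.0% | 94.6% | 92.9% | 91.1% |

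Table 9 fits 10% loss in both arms, with 64/32 closest. The no-loss row is more than 2 points too high in every cell.

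**Step 2: which sample size lies behind the ~92% (effect -0.2, SD 2.6)?**

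| n per arm | SE | 1.8/SE | Power |
|---|---|---|---|
| 72/36 (no loss) | 0.531 | 3.39 | 91.9% |
| 64/32 | 0.563 | 3.20 | 88.6% |
| 65/32 | 0.562 | 3.21 | 88.7% |
| 64.8/32.4 | 0.559 | 3.22 | 89.0% |
| 65/33 | 0.556 | 3.24 | 89.4% |

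The stated figure is reproduced only with no loss.

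**Step 3: can one sample size give both figures?** At SD 2.6 and 2:1:

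| Total evaluable | Power, effect 0 | Power, effect -0.2 |
|---|---|---|
| 94 | 93.6% | 87.9% |
| 96 | 94.0% | 88.6% |
| 100 | 94.8% | 89.8% |
| 107 | 96.0% | 91.7% |
| 108 | 96.2% | 91.9% |

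A printed 94%, whether rounded or truncated, needs about 94 to 100 children. There the tipping-point power is 87.9% to 89.8%. A power that rounds to 92% needs at least 107, where Table 9 would show 96%. The two ranges do not meet, so the conclusion does not depend on guessing the exact number used.

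**Step 4: which of the printed figures is out of line?** The per-protocol power at 60/30 is: SE = 2.6 × √(1/60 + 1/30) = 0.581, noncentrality 2/0.581 = 3.44, power 92.5% (stated 92%). Table 9 and the per-protocol figure both reduce the sample for loss. Only the tipping-point figure does not.

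**The case against.** The best defence is that ~92% was computed on purpose for all 108 children. It reproduces on 72/36, and Protocol 9.4.2 says every child in the full analysis set can be viewed as included in this analysis. However, that statement says only that children with missing data count towards the missing fractions f1 and f0. It adds no precision, and the same paragraph keeps the standard error of the missing-at-random analysis, which is the analysis that Table 9 describes.

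Other points, and what stands of them:

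- **Fit to Table 9.** At 64/32 the SD 2.5 cell is 95.5%, printed as 95%, so the match needs truncation rather than rounding. The per-protocol 92.5% printed as 92% suggests the same. The 65/33 split fits least well (91.1% against 90%). The splits that do fit under truncation give 88.6% to 89.0%. This stands, and does not move the answer from about 89%.
- **SD.** The tipping-point sentence names no SD. At SD 2.5 with 65/33 the power would be 91.5%, but 2.6 is the chosen planning value and 65/33 is the poorest match to Table 9.
- **Loss in the somapacitan arm only.** 64.8/36 gives 91.0%. This is still below the stated figure and contradicts the equal-loss assumption.
- **The mixed model.** Children without week-52 data contribute through earlier visits, so the t-test powers are approximations. This stands, but any gain would raise both figures and would not reconcile them.

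**Conclusion.** The ~92% is wrong as written. On the basis that reproduces Table 9, the tipping-point power is about 89% (88.6% to 89.4% across the possible whole-number splits), an overstatement of about 3 points. The penalty costs about 5 points (94% to about 89%), where the text implies 2.

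This rests on SD 2.6, 10% loss in each arm, the two-group t-test named in the plan, and the plan's own rule that the standard error is unchanged. The sample sizes are inferred by fitting Table 9, because the documents do not state them. The incompatibility of 94% and ~92% at SD 2.6 holds whatever total is chosen.

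The consequence is minor. The sample size of 108, the 94% primary power and the non-inferiority rule are unaffected, and the tipping-point analysis has no target power and no pass/fail criterion.

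**What to change.** In Protocol 9.2 and SAP 5, replace ~92% with ~89%. Keep the 2 cm/year penalty and the -0.2 cm/year adjusted effect. State the evaluable number per arm and the SD behind both Table 9 and the tipping-point power, so that a reader can reproduce each. If the sponsor did intend all 108 children for the tipping-point figure, the text should say that it assumes no loss of information and so differs in basis from Table 9.

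The cost is one restated number and a line of stated assumptions in each document. It needs no extra children and no change to any analysis.

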### 9.3      Populations for analyses

The following populations are defined:

Population	Description
Full analysis set	Full analysis set (FAS): All subjects randomised. Exclusion of data from analyses should be used restrictively, and normally no data should be excluded from the FAS. Subjects will be analysed according to the randomised treatment
Safety analysis set	Safety analysis set (SAS): All subjects randomly assigned to trial treatment and who take at least 1 dose of trial product. Subjects are analysed according to the treatment they actually received.
Per protocol analysis set	PP: Subjects from FAS who have not violated any inclusion/exclusion criteria and have used the randomised treatment for at least 47 weeks (for subjects receiving somapacitan) or 329 days (for subjects receiving Norditropin) corresponding to 90% of the planned exposure. Subjects are analysed according to the treatment they actually received.

The subjects or observations to be excluded, and the reasons for their exclusion must be documented before unblinding. The subjects and observations excluded from analysis sets, and the reason for this, will be described in the CTR. Two observation periods are defined:

- on-treatment: from first administration and up until last trial contact, visit 7 or 14 days after last administration, whichever comes first
  - in-trial: from first administration and up until last trial contact or visit 8, whichever comes first
- Analysis based on the 'in-trial' observation period is to be viewed as supplemental analysis to the analysis based on the 'on-treatment' analysis.

## 9.4 Statistical analyses

If necessary, a statistical analysis plan (SAP) may be written in addition to the protocol. The SAP will be finalised prior to first subject first visit, and it will include a more technical and detailed description of the statistical analyses described in this section. This section is a summary of the planned statistical analyses of the most important endpoints including primary endpoint.

### 9.4.1 General considerations

The one-sided test used for the primary endpoint is based on an alpha level of 2.5%. All other statistical tests conducted will be two-sided on the 5% significance level.

Two factors are defined as follows:

- Age group: Age at randomisation (<6 versus  $\geq 6$  years)
- GH peak group: Growth hormone peak level (< 7 versus  $\geq 7$  ng/ml)

All efficacy endpoints will be analysed using FAS and all safety endpoints will be analysed using SAS. The primary endpoint will additionally be analysed using PP as a support to the results achieved using FAS under the hypothetical strategy.

### 9.4.2 Primary endpoint(s)

The primary endpoint:

- Height velocity (cm/year) at week 52

will be derived from height measurements taken at baseline and the week 52 visit (landmark visit) in the following way:

$HV = (\text{height at 52 weeks visit} - \text{height at baseline}) / (\text{time from baseline to 52 weeks visit in years})$ .

Annualized HV at the intermediate visits: Week 13, 26 and 39, will be derived analogously to the week 52 HV:  $HV = (\text{height at } j \text{ weeks visit} - \text{height at baseline}) / (\text{time from baseline to } j \text{ weeks visit in years})$ ,  $j=13, 26, 39$ .

The primary analysis of the primary endpoint addressing the primary estimand described in section 3.1 is based on the FAS but data assessed after discontinuation of randomised treatment will be disregarded in the analysis.

In order to estimate the primary estimand, a mixed model for repeated measurements (MMRM) with an unstructured covariance matrix is conducted on HV data (annualized HV at planned visits at week 13, week 26, week 39 and week 52) up to discontinuation of randomised treatment for each treatment arm using all randomised subjects and assuming missing at random (MAR) for both treatment arms. The MMRM will include sex, age group, GH peak group and sex by age group interaction term as factors and baseline height as a covariate, all nested within week as a factor. From this analysis an estimate of the treatment difference at week 52 with corresponding 95% CI will be presented.

Non-inferiority of somapacitan will be considered confirmed if the lower boundary of the two-sided 95% confidence interval is above -2 cm/year.

A tipping point analysis will be conducted as a sensitivity analysis for the analysis of the primary endpoint for the primary estimand. For this analysis, the missing data are expected to be mainly due to subjects that are withdrawn from the trial or discontinue randomised treatment. The sensitivity analyses described below will be used to investigate whether the results from the primary analysis are robust against departures from the assumption of MAR.

Let  $\delta$  be defined as the difference between the mean of the observed data and the mean of the unobserved data  $\mu_{\text{obs}} - \mu_{\text{unobs}}$ , adjusted for other observed data. Under an MAR analysis,  $\delta$  is assumed to be 0. Positive values of  $\delta$  indicate that subjects with missing endpoint values have smaller HV than subjects with observed endpoint values. If subjects primarily withdraw or discontinue randomised treatment/start ancillary therapy due to a perceived lack of efficacy, then this could be the most likely direction of departure from MAR. Let  $f_1$  and  $f_0$  be the fractions of subjects with unobserved endpoint data in the somapacitan and Norditropin® arms, respectively. The sensitivity analysis is done by subtracting a quantity  $\Delta$  from the treatment effect estimate under the MAR assumption, where  $\Delta = f_1\delta$  if data depart from MAR in the somapacitan arm only,  $\Delta = -f_0\delta$  if data depart from MAR in the Norditropin® arm only, and  $\Delta = (f_1 - f_0)\delta$  if data depart from MAR in the same way in both arms. The calculations for the 3 scenarios will use a range of  $\delta$  values increasing from 0 until the resulting 95% CI no longer is completely above -2cm/year for the most conservative evaluation (data depart from MAR in the somapacitan arm only) and the approximation that the standard error of the treatment difference is unaffected by the sensitivity analysis. All subjects from the FAS can be viewed as included in this analysis as subjects with missing endpoint data will be contributing to one of the fraction values  $f_1$  and  $f_0$ .

An analysis of the primary endpoint using the same analysis model as was used for the primary analysis under the primary estimand but based on PP instead of FAS will be conducted as a supplementary analysis.

#### **9.4.3 Secondary endpoint(s)**

##### **9.4.3.1 Confirmatory secondary endpoint(s)**

NA

##### **9.4.3.2 Supportive secondary endpoints**

**Table 10 Efficacy**

Endpoint title	Time frame	Unit
Change in bone age	From visit 1 to week 52	Years
Change in Height Standard Deviation Score	From baseline (week 0) to week 52	-10 to +10
Change in Height Velocity Standard Deviation Score	From baseline (week 0) to week 52	-10 to +10

The efficacy endpoints will be analysed based on the ‘on-treatment’ observation period and the ‘in-trial’ observation period within the trial period (52 weeks of treatment).

Height SDS will be derived using Chinese general population standards and HV SDS will be derived using Prader standards as reference data.

Change in height SDS and HV SDS will be analysed using the same analysis model as was used for analysing the primary endpoint for the primary estimand except for using baseline height SDS and baseline HV SDS, respectively, as a covariate in the model instead of baseline height. The estimate for the treatment difference at week 52 will be reported with corresponding 95% CI and p-value.

Bone age will be analysed using an ANCOVA model on bone age/chronological age assessed at week 52 and the model will include treatment, sex, age group, GH peak group and sex by age group interaction term as factors and baseline bone age/chronological age as a covariate. The treatment difference estimate will be reported with corresponding 95% CI and p-value.

**Table 11 Safety**

Endpoint title	Time frame	Unit
Change in fasting plasma glucose	From baseline (week 0) to week 52	mmol/l
Change in HbA1c	From baseline (week 0) to week 52	%

The safety endpoints will be analysed using descriptive statistics based on the ‘on –treatment’ observation period and the ‘in-trial’ observation period.

**Table 12      Pharmacodynamics**

Endpoint title	Time frame	Unit
Change in IGF-I Standard Deviation Score	From baseline (week 0) to week 52	-10 to +10
Change in IGFBP-3 Standard Deviation Score	From baseline (week 0) to week 52	-10 to +10

The PD endpoints will be analysed based on the ‘on –treatment’ observation period and the ‘in-trial’ observation period.

Change in IGF-I SDS and IGFBP-3 SDS will be analysed using an MMRM with an unstructured covariance matrix on all relevant post-baseline change from baseline values as dependant variables. The model will include treatment, sex, age group, region, GH peak group and sex by age group interaction term as factors and baseline value as a covariate, all nested within week as a factor. From the MMRM, the treatment difference at Week 52 will be estimated and the corresponding 95% CI and p-value will be reported for each endpoint.

#### **9.4.4      Other safety analyse(s)**

All safety analyses will be made on the safety analysis set. The standard safety assessments (AEs, safety laboratory parameters, vital signs, etc.) will be analysed using descriptive statistics based on the ‘on –treatment’ observation period. Additionally, AEs will also be analysed using descriptive statistics based on the ‘in-trial’ observation period.

